5. STATISTICAL CONSIDERATION

5.1 Statistical Analysis Principle

The analysis will be based on the intent-to-treat (ITT) principle. For all study outcomes, the comparison will be conducted in all randomized participants based on their randomisation group results. All comparisons will be two-sided and statistical significance is defined as P<0.05.

5.2 Participation and Withdrawal Data

All participants who sign informed consent and attend baseline assessment will be included in the study analysis. The flow of participants through the study will be graphically displayed using a CONSORT diagram. The study will outline the dataset, number and proportions of participants who withdrawal and lost-to-follow-up, including (but not limited to):

Number of patients screened;

Number and proportions of patients in the intervention and control group; Number and proportions of patients that do not meet the inclusion criteria; Number and proportions of patients that complete the trial; Number and proportions of patients that drop out of the trial.

5.3 Handling of Missing Data and Outliers

When data are missing, we will report the number of observations and assess the presence of specific missingness patterns. The analysis will be performed on the complete-case records without any imputation (i.e. the participant has a missing value for a variable required for a model will be excluded from that analysis).

Due to the rigorous data query during the whole process of data collection in the trial, outliers will be not determined in the primary statistical analysis.

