3.6 Outcome Evaluation

The information of study outcomes (for participants in both intervention and control groups) was collected at baseline and each follow-up visits at 3th month, 6th month, 9th month, and 12th month. All the data collection was conducted using standardized equipment and following uniform operational protocols. These data were collected in three ways: (1) standardized electronic questionnaire interview; (2) physical examination; (3) fingertip blood sample collection.

The primary outcome, 10-year risk of ASCVD, was calculated by the China-PAR prediction model based on age, sex, geographic region (northern/southern China), urbanity, waist circumference, systolic blood pressure (SBP), use of antihypertensive

medication, presence of diabetes, total cholesterol (TC), high-density lipoprotein cholesterol (HDL-C), smoking status, and family history of ASCVD.

Regarding assessment of the metabolic risk factors, to be more specific, blood pressure was measured twice on the right upper arm using a standard sphygmomanometer (Omron HEM-7121, Omron Corporation, Japan) after 5 minutes of rest in the sitting position. Blood glucose and blood lipid were tested by the rapid blood glucose analyser (BeneCheck BK6-20 M Multi-Monitoring System, Suzhou Pu Chun Tang Biotechnology, China) and the fast photochemical lipid analyser (CardioChek PA Analyzer; Polymer Technology Systems, USA), respectively. Body mass index (BMI) was calculated as body weight in kilograms divided by the squared value of height in meters, with obesity was defined as a BMI≥28.0 kg/m².

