APPENDIX 4:

ANALYSIS CODE FOR THE STUDY

* Compare Baseline Characteristics; * continuous variables; proc means data=smarter data mean std; var IS age SBP0 DBP0 GLU0 NHDL0 waist0 BMI0 risk0 risk lifetime 0; by group; run; * categorical variables; proc freq data=smarter data; tables male pd education pd labor pd income pd married pd insure smk daily 0 PA 1t3000 0; by group; run; * Evaluation of Research Outcomes; data fu4 data; set smarter data; if risk4^=.; run; proc means data=fu4 data n mean std; var risk0 risk4 risk lifetime 0 risk lifetime 4 SBP0 SBP4 DBP0 DBP4 GLU0 GLU4 NHDL0 NHDL4; by group; run; proc freq data=fu4 data; tables obesity 0 obesity 4 smk daily 0 smk daily 4 PA lt3000 0 PA lt3000 4 LTPA0 LTPA4; by group; run; proc means data=fu4 data n mean clm; var risk4_change risk_lifetime4_change SBP4_change DBP4_change GLU4_change NHDL4 change; by group; run;

* model for continuous variables (eg.10-y ASCVD risk);

proc glimmix data=fu4_data;

class village_id group(ref='2') male education_high_above Last_year_income_lt_10k
occupation_farmer marriage_yes insure_yes vc_risk_grp vc_sbp_grp vc_age_grp
doctor_college_above;
model risk4_change=group risk0 IS_age male education_high_above
Last_year_income_lt_10k occupation_farmer marriage_yes insure_yes vc_risk_grp
vc_sbp_grp vc_age_grp doctor_college_above
/solution dist=normal link=identity ddfm=bw cl ;
random int/subject=village_id type=un;
run;

* model for categorical variables (eg.smk daily);

proc glimmix data=fu4_data;

class village_id group(ref='2') male education_high_above Last_year_income_lt_10k
occupation_farmer marriage_yes insure_yes smk_daily_0 vc_risk_grp vc_sbp_grp
vc_age_grp doctor_college_above;
model smk_daily_4(event="1") =group smk_daily_0 IS_age male education_high_above
Last_year_income_lt_10k occupation_farmer marriage_yes insure_yes vc_risk_grp
vc_sbp_grp vc_age_grp doctor_college_above/solution dist=binary link=logit ddfm=bw cl;
random int/solution subject=village_id type=un;
ods output ParameterEstimates=Coefficients_smk;
run;

data coefficients_smk; set coefficients_smk; if effect~='Intercept' then do; PA_OR=exp(Estimate); PA_OR_L=exp(Estimate-1.96*stderr); PA_OR_U=exp(Estimate+1.96*stderr); PA_OR_95CI=compress(put(PA_OR,4.2))||"("||compress(put(PA_OR_L,4.2))||","||compress(p ut(PA_OR_U,4.2))||")"; end; run; * Subgroup Analysis;

* eg.sex: male/female;

data male; set fu4_data; if male=1; run; data female; set fu4_data; if male=0; run;

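### The SAP promises a comparison of all randomised participants but specifies complete cases, and the Appendix 4 code is stricter still: one filter on the 12-month risk score governs every outcome it covers (minor).

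*Combined protocol and SAP*

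**What the plan says.** Three sections of the SAP define who is analysed.

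- SAP 5.1: "For all study outcomes, the comparison will be conducted in all randomized participants based on their randomisation group results".
- SAP 5.2: "All participants who sign informed consent and attend baseline assessment will be included in the study analysis".
- SAP 5.3: "The analysis will be performed on the complete-case records without any imputation". The parenthesis that follows sets the scope: "the participant has a missing value for a variable required for a model will be excluded from that analysis". The exclusion therefore applies model by model. The section also undertakes to report the number of observations and to look at patterns of missingness.

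The Appendix 4 code builds a single file for outcome evaluation: "data fu4 data; set smarter data; if risk4^=.; run". The variable `risk4` is the 12-month 10-year ASCVD risk. The descriptive steps for every primary and secondary outcome and for leisure-time activity read this file. So do the two example models ("proc glimmix data=fu4_data") and the interaction test, and the sex subgroups are cut from it.

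SAP 3.6 says that outcome information "was collected at baseline and each follow-up visits at 3th month, 6th month, 9th month, and 12th month". The primary model has a single response per participant, the 12-month change: "model risk4_change=group risk0 IS_age male education_high_above". Its only random term is a village intercept.

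**The concern.** There are three separate problems.

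1. **Label.** An analysis that leaves out participants with missing values does not compare everyone randomised. 5.1 and 5.2, read literally, cannot both hold alongside 5.3.
2. **Code against plan.** 5.3 would let each outcome use its own observed data. The `risk4` filter does not. By SAP 3.6 the score needs waist circumference, SBP, treatment, diabetes status, total cholesterol, HDL-C, smoking and other inputs. One failed fingertip lipid test at month 12 could therefore remove valid blood pressure, smoking and activity data. SAP section 1 asks for deviations to be described and justified, and no reason is given for this one.
3. **No fallback.** Someone seen at month 9 but not at month 12 contributes nothing to the comparison. Complete-case analysis is unbiased only if missingness is unrelated to outcome given the covariates. The plan allowed for 10% loss but contains no analysis that tests this. The one sensitivity analysis shown (Table S6) removes participants with MACEs, which is a further exclusion.

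**Working it through.** **Reproducing the stated power (SAP, Sample Size).** Inputs: difference 1.0, SD 6.0, two-sided 0.05, ICC 0.06, 4533 participants in 127 villages, and an assumed equal split of 2266.5 per arm. Design effect DE = 1 + (m − 1) × ICC; effective n per arm = n / DE; normal approximation.

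- No loss: m = 4533/127 = 35.7, DE = 3.08, power 89.2%.
- 10% loss within villages: m = 32.1, DE = 2.87, power 88.2%. This matches the stated 88%.
- 4475 analysed (the Table S5 total at 12 months): power 89.1%.

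Missing data at the level seen in the tables cost about 0.1 point of power.

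**How much is missing at 12 months.** Table S5 covers participants with hypertension, diabetes or dyslipidaemia.

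| Visit | Intervention missing (of 2287) | Control missing (of 2212) |
|---|---|---|
| 3 months | 29 | 15 |
| 6 months | 31 | 5 |
| 9 months | 28 | 9 |
| 12 months | 12 | 12 |

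At 12 months, 24/4499 = 0.53% are missing (0.52% and 0.54% by arm). The hypertension rows of Table S4 agree: 2222/2234 = 99.5% and 2144/2156 = 99.4% present. These are medication data, so they stand in for a missing visit and do not count missing risk scores directly.

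**Ceiling.** Table S6 holds 2246 + 2188 = 4434. 4533 − 4434 = 99, or 2.2%, and this includes participants removed on purpose because of MACEs. The 12-month percentages in Table S6(a) reproduce on one denominator per arm (449/2246 = 20.0% and 462/2188 = 21.1% smoking daily; 1040/2246 = 46.3% with insufficient leisure-time activity). That fits the common filter.

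**Size of a possible bias.** Suppose the participants missing in one arm differ from completers by d in their change, and those missing in the other arm do not. Bias = f × d, where f is the fraction missing in that arm. With d = 3 points (an assumption; the documents give no value):

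- f = 10% (planning allowance): 0.30 points, against a design difference of 1.0
- f = 2.2% (ceiling): 0.07 points
- f = 0.53% (Table S5): 0.016 points

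The ceiling need not split evenly. From the Table S5 baseline counts, at least 2287 − 2246 = 41 intervention and 2212 − 2188 = 24 control participants are absent from Table S6, which leaves 99 − 65 = 34 unplaced. If all 34 were in the intervention arm, f = 75/2321 = 3.2% and the bias is 0.10.

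The net difference in Table S6(a) is −1.88 (−2.57 to −1.19), a half-width of (2.57 − 1.19)/2 = 0.69. To move the −1.19 limit to zero, the missing participants in one arm would have to differ by 1.19/0.0053 ≈ 225 points (impossible), by 1.19/0.022 ≈ 55 points at the ceiling, or by 1.19/0.10 ≈ 12 points at 10% loss.

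**The case against.** The case for leaving the plan alone is fair in several respects.

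- **The wording of 5.1 can be read as analysis by assigned group**, with 5.3 openly stating how missing values are treated. This stands: nothing is hidden. What remains is an inaccurate description of the analysis set, which rewording would cure.
- **The primary outcome is the change to 12 months**, so a model of month 12 alone matches the estimand. This stands. It is not an error, and results already appear in the appendix, so replacing the primary model now would be post hoc.
- **Interim visits would add little.** This stands too. With about 0.5% missing at month 12 the gain in precision is negligible, and in Table S5 the interim visits are less complete and less balanced than month 12. How many of those missing at month 12 have an interim value is not shown.
- **The participant with blood pressure but no lipid result is hypothetical.** The documents do not show that one exists. That limits the impact, but the code still departs from 5.3.

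Two stronger readings are tempting. A reader might infer that the filter affects every outcome in the trial. The documents do not show that: no code is given for MACEs or medication adherence, and the models shown, for 10-year risk and daily smoking, are labelled as examples. A reader might also infer that the quarterly data were wasted. In fact they are reported in Tables S4 and S5 and were used to update participants' risk portraits and goals. They are absent only from the outcome models shown.

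**Conclusion.** The point holds as a minor one. SAP 5.1 and 5.2 describe a population that 5.3 does not deliver, and the Appendix 4 filter is stricter than 5.3 for the outcomes it covers. No planned analysis tests the complete-case assumption.

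The likely shift in the primary estimate is about 0.02 to 0.07 points, or 0.10 if the unplaced participants all fall in the intervention arm, against a confidence half-width of 0.69. This rests on the assumed 3-point difference, on Table S5 as a guide to missing 12-month visits, and on Table S6 as an upper bound. The main-analysis estimate, the randomised arm sizes and the number dropped solely for a missing `risk4` are not in the documents. They give no ground for saying that the trial's conclusion would change.

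**What to change.** 1. Replace the global `risk4` filter with a filter for each outcome, as 5.3 already states, and report the number analysed per outcome and arm, including how many the single filter had removed.
2. Reword 5.1 and 5.2 to say that available cases are analysed by randomised group.
3. Keep the 12-month change model as primary. Add, as a sensitivity analysis, a repeated-measures linear mixed model on the 3-, 6-, 9- and 12-month values with group by visit, the baseline value, the same covariates and minimisation factors as the coded model, and village and participant effects. Report its 12-month contrast. Because results exist, record it as an addition, with the reason.

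Items 1 and 2 cost a line of code, a rerun and a change of wording. Item 3 needs some reprogramming, a chosen covariance structure and a missing-at-random assumption. It also still leaves out anyone with no post-baseline value, so the description in item 2 is needed either way. None of this alters the sample-size figures.

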5.4 Statistical Analysis Software

The analyses will be performed using SAS 9.4 (SAS Institute Inc., Cary, NC, USA).

6. STATISTICAL ANALYSES

6.1 Baseline Characteristics

Descriptive statistics will be used to summarize the baseline characteristics of the whole cohort of the study participants and by study groups: continuous variables will be presented as mean and standard deviation, or medians, interquartile range, minimum and maximum, and categorical variables as frequencies and percentages.

T-test/Wilcoxon rank sum test will be used to compare continuous variables between the intervention and control group. The Chi-square test/Fisher exact test will be used to compare the categorical variables between the two groups.

6.2 Adherence to Intervention

The adherence to village doctor-led health management strategies in the intervention group was monitored using an automated system since the first follow-up visit (at 3 months). Thet study will report monthly data of the short video view rate, smart band wearing rate, and daily step target achieving rate.

Satisfaction of the intervention participants with the health education short videos was inquired at each stage follow-up visits. We will report the proportion of participants who believed the short videos were relevant to their health conditions, the proportion of participants who believed the short videos were rather useful, and the proportion of participants who expressed willingness continue receiving short videos of the trial after the study was ended.

6.3 Analysis of Primary Outcomes

The primary outcome of the trial is the mean changes in 10-year risk of ASCVD based on the China-PAR model from baseline to the 12 months. Linear mixed effects model will be used to compare the primary outcome between the intervention group and the control group. The dependent variable is the change in 10-year risk of ASCVD of the participants from baseline to the 12-month, and the independent variable is the study group. Villages will be adjusted in the model as a random effect. The net difference between the two groups was assessed by the model, with multivariable adjustment by baseline covariates including age, sex, education, occupation, annual household income, marital status, and social medical insurance.

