3.3 Randomisation and Blinding

The group assignment was conducted by a central randomisation system based on minimisation algorithm. The villages served as the units of randomisation. The assignment was stratified by county, and was conducted after all participants within each county had been recruited and baseline survey data had been collected. Factors that were balanced between the comparison groups include participants' age, systolic blood pressure, and 10-year risk of ASCVD, as well as the education attainment of the village doctor. Random numbers were generated by an independent statistician using a computer. A random element of 0.9 were introduced to enhance unpredictability in the allocation process.

Due to the nature of the cluster design and the intervention programme, the village doctors and the study participants were aware of their group allocation. However, the allocation will be concealed from the study statisticians.

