6.4 Analysis of Secondary Outcomes

The secondary outcomes included mean changes in the levels of lifetime risk of ASCVD based on the China-PAR model, SBP, DBP, FBG, and non-HDL-C, as well as changes in the proportions of obesity, daily smoking, and insufficient physical activity, from baseline to the 12 months. The assessment of secondary outcomes of continuous variables will be analysed using linear mixed effects models, same as the analysis method of primary outcome, and the categorical variables will be analysed using the generalised linear mixed effects models. Villages will be adjusted in the

models as a random effect. The net differences between the two groups were assessed by the models, with multivariable adjustment by baseline covariates including age, sex, education, occupation, annual household income, marital status, and social medical insurance.

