Insufficient leisure-time activity (<150/75 min/wk)	1541 (68.6%)	1040 (46.3%)	-22.3% (-24.7% to -19.9%)	1420 (64.9%)	1372 (62.7%)	-2.2% (-4.5% to 0.1%)	0.38 (0.24 to 0.59)	< 0.001

* Data were mean (SD), n (%), mean (95%CI) or OR (95%CI) unless otherwise stated.

All net group difference was adjusted for clustering effects by villages (as random effect), four minimisation factors, age, sex, education, occupation, annual household income, marriage status, social medical insurance, and baseline level of the outcome.

	Interv	ention (n=2246)	Co	ntrol (n=2188)	Net Group Difference	D l	D :
Subgroup	Number	Changes (95%CI)	Number	Changes (95%CI)	(95%CI)	P value	P-inter
Age, year							0.73
<60	1352	-7.0 (-7.3 to -6.6)	1301	-5.2 (-5.6 to -4.9)	-1.86 (-2.57 to -1.16)	< 0.001	
≥60	894	-5.2 (-5.6 to -4.8)	887	-2.7 (-3.1 to -2.3)	-1.82 (-2.63 to -1.01)	< 0.001	
Sex							0.03
Male	1130	-7.2 (-7.6 to -6.7)	1062	-4.6 (-5.0 to -4.2)	-2.20 (-3.05 to -1.36)	< 0.001	
Female	1116	-5.4 (-5.7 to -5.1)	1126	-3.8 (-4.1 to -3.5)	-1.55 (-2.20 to -0.90)	< 0.001	
Education							0.74
Below high school	1755	-6.0 (-6.3 to -5.7)	1749	-4.1 (-4.4 to -3.9)	-1.83 (-2.54 to -1.12)	< 0.001	
High school and above	491	-7.3 (-7.9 to -6.7)	439	-4.4 (-5.0 to -3.7)	-2.11 (-3.03 to -1.20)	< 0.001	
Occupation							0.03
Farmer	1535	-6.1 (-6.4 to -5.8)	1465	-4.4 (-4.7 to -4.0)	-1.63 (-2.41 to -0.85)	< 0.001	
Non-farmer	711	-6.6 (-7.1 to -6.1)	723	-3.8 (-4.3 to -3.4)	-2.60 (-3.37 to -1.83)	< 0.001	
Annual household income, yuan							0.02
<10 000	358	-5.1 (-5.8 to -4.5)	347	-2.4 (-3.1 to -1.8)	-2.76 (-3.90 to -1.63)	< 0.001	
≥10 000	1888	-6.5 (-6.8 to -6.2)	1841	-4.5 (-4.8 to -4.2)	-1.72 (-2.40 to -1.03)	< 0.001	
10-year risk of ASCVD, %							< 0.001
<16	1128	-3.5 (-3.7 to -3.3)	1128	-2.3 (-2.6 to -2.0)	-1.14 (-1.76 to -0.52)	< 0.001	
≥16	1118	-9.0 (-9.5 to -8.6)	1060	-6.2 (-6.6 to -5.8)	-2.57 (-3.42 to -1.72)	< 0.001	

 Table S6 (b). Subgroup results of the primary outcome (sensitivity analysis: excluding participants with MACEs)

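### The SAP's model text omits the baseline outcome and three of the four minimisation factors, while the published code and footnotes include them, so two primary models are on record

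*Combined protocol and SAP*

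**What the plan says.** Protocol 4.2 leaves the analysis detail to the SAP, so SAP section 6 is where the model should be fixed.

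- **SAP 6.3, primary outcome.** "The dependent variable is the change in 10-year risk of ASCVD of the participants from baseline to the 12-month". Study group is the independent variable, village is a random effect, and the adjustment is described as "multivariable adjustment by baseline covariates including age, sex, education, occupation, annual household income, marital status, and social medical insurance".
- **SAP 6.4, secondary outcomes.** Continuous outcomes follow 6.3. For the rest, "categorical variables will be analysed using the generalised linear mixed effects models", with the same seven covariates. No link function, dependent variable or baseline-status term is named.
- **SAP 3.3, allocation.** Villages were minimised on four factors: participants' age, plus "systolic blood pressure, and 10-year risk of ASCVD, as well as the education attainment of the village doctor". Also, "The assignment was stratified by county".
- **Appendix 4, code.** The primary model begins "model risk4_change=group risk0 IS_age male education_high_above" and goes on to include `vc_risk_grp`, `vc_sbp_grp`, `vc_age_grp` and `doctor_college_above`. The binary example models `smk_daily_4` with a logit link and `smk_daily_0` as a covariate.
- **Appendix 3, Table S6(a) footnote.** "All net group difference was adjusted for clustering effects by villages (as random effect), four minimisation factors, age, sex, education"; the sentence ends by adding the baseline level of the outcome. The Table S5 footnote says the same.
- **SAP section 1.** Reported results should follow the SAP, and departures must be described and justified in the final report.

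**The concern.** The SAP text and the code give different right-hand sides for the primary analysis. A reader cannot tell which model was pre-specified.

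The omitted terms matter. Change in risk depends strongly on starting risk. In Table S6(b) the control arm fell by 2.3 points where baseline risk was below 16% and by 6.2 points where it was 16% or more. A change score without the baseline value therefore carries any chance difference in baseline risk into the estimated effect, and leaves explainable variance in the residual. The minimisation factors were judged important enough to drive allocation, so an analysis would normally condition on them.

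For the binary secondary outcomes the gap is one of specification. SAP 6.4 speaks of changes in proportions but does not say what is regressed on what. The code had to make that choice.

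**Working it through.** **1. Terms side by side**

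| Term | SAP 6.3/6.4 | Code and footnotes |
|---|---|---|
| Baseline value of outcome | no | yes (`risk0`, `smk_daily_0`) |
| Minimisation: age | yes | yes, plus `vc_age_grp` |
| Minimisation: 10-year risk | no | yes (`vc_risk_grp`) |
| Minimisation: systolic pressure | no | yes (`vc_sbp_grp`) |
| Minimisation: doctor's education | no | yes (`doctor_college_above`) |
| Six other listed covariates | yes | yes |
| Village random intercept | yes | yes |
| County (stratification) | no | no |

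The education in the SAP list is the participant's, because the code carries `education_high_above` separately from `doctor_college_above`. For the primary outcome, baseline 10-year risk is both the baseline outcome and a minimisation factor, so three distinct variables are missing, not four. The `vc_` prefix is undefined; if it marks village-level categories, even age is not entered in the SAP as it was minimised. Three of four is the cautious count.

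**2. The plan's own power figure**

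The SAP's sample size section gives 88% power for 4533 participants in 127 villages at ICC 0.06. With a difference of 1.0, SD 6.0 and 10% loss, m = 0.9 × 4533/127 = 32.1 and the design effect is 1 + 31.1 × 0.06 = 2.87. Power is 88.2%, so the figure reproduces. It does not depend on the covariate list.

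**3. Dependence of 12-month risk on baseline risk, from Table S6(a)**

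Inputs (baseline SD, 12-month SD, 95% CI of change):
- Intervention, n = 2246: 7.1, 5.8, -6.5 to -6.0.
- Control, n = 2188: 6.8, 6.9, -4.5 to -3.9.

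The code takes these intervals from `proc means` with `clm`, so they ignore clustering.

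- SD of change = half-width/1.96 × √n: 0.25/1.96 × √2246 = 6.04 and 0.30/1.96 × √2188 = 7.16.
- r = (SD0² + SD12² − SDc²)/(2·SD0·SD12) = 0.58 and 0.45.
- Slope = r × SD12/SD0 = 0.47 and 0.46, so about 0.47 for a common slope. Rounding of the printed intervals allows 0.26 to 0.63 across the arms.

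**4. Effect of the baseline difference**

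- Crude difference in change: -6.3 − (-4.2) = -2.1.
- Baseline-adjusted: (11.7 − 13.5) − 0.47 × (18.0 − 17.7) = -1.94.
- Shift: 0.3 × (1 − 0.47) = 0.16 points towards the intervention, about 8% of the effect (0.16/2.1).
- Rounding of the two baseline means lets the imbalance be 0.2 to 0.4, so the shift runs from 0.2 × (1 − 0.63) = 0.07 to 0.4 × (1 − 0.26) = 0.30.
- Table S6(a) reports -1.88 from the full adjustment set.

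**5. Precision**

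The pooled SD of change is about 6.6. With a common baseline slope the residual SD is about 5.5, a variance ratio of 0.69 (0.60 to 0.76 over rounding). If the ICC stayed at 0.06 with 4434 analysed (an assumption), power for a 1.0-point difference would rise from about 82% (69 to 94%) to about 94% (88 to 98%).

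The reported result does not show this gain. Its SE is (2.57 − 1.19)/(2 × 1.96) = 0.35. A crude change score at ICC 0.06 would give 6.6 × √(2 × 3.03/2217) = 0.345. With residual SD 5.5, the reported SE would correspond to an ICC near 0.10.

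**The case against.** The strongest reply is that this is a reporting inconsistency around two valid models.

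- **Validity.** A reader might infer that the SAP-text model is biased or invalid. It is not. Under randomisation a change score without baseline is unbiased, and leaving out minimisation factors usually makes intervals too wide. The 10% entry threshold applied to both arms before allocation, so regression to the mean matters only through the chance imbalance already counted. This stands.
- **Conclusion.** With SE 0.345 the crude -2.1 gives z of about 6. At an assumed ICC of 0.15, z is still about 4.3. This stands.
- **Model selection.** A reader might infer that the coded model was chosen for its result. The documents do not support that: -1.88 is nearer the null than the crude -2.1, and SAP 3.3 says allocation would be concealed from the statisticians.
- **Comparator.** The 0.16 points compare a crude change score with adjustment for baseline alone. The SAP model already adjusts for age and sex, both inputs to the China-PAR score, and may absorb part of the imbalance. This stands; 0.16 is not the SAP-versus-code difference.
- **Source.** Table S6(a) excludes participants with MACEs. The main results table is not in these documents, so which model produced the headline estimate is inferred from the code and footnotes. Nor is the final report here, so a failure to disclose is not established. Both stand.
- **Open list.** The word before the covariates in SAP 6.3 could make the list open-ended. This is weak: a list that names marital status and insurance but not the baseline outcome does not pre-specify the latter, and an open list leaves the primary model undefined.

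**Conclusion.** The discrepancy is established by direct comparison of the texts: SAP 6.3 and 6.4 omit the baseline outcome, and also systolic pressure, 10-year risk and doctor's education as minimisation factors; the code and the Table S5 and S6(a) footnotes include them. Two primary models are on record, and no justification for the change appears in these documents. County, the stratification factor, is in neither.

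The SAP-text model is valid but less well protected against chance imbalance and expected to be less precise. The scale is about 0.16 points (about 0.07 to 0.30) in favour of the intervention for a crude change score against baseline adjustment. That rests on SDs backed out of rounded, unclustered intervals in a sensitivity table. The exact difference between the two recorded models and the realised gain in precision cannot be computed from what is given. This should be fixed for transparency of the primary analysis; the finding of benefit does not turn on it.

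**What to change.** Results exist, so the SAP should not be silently rewritten to match the code. In a dated amendment, or as a declared deviation under SAP section 1 with its reason:

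1. State that the primary model regresses the 12-month value (or the change) on group, the baseline value of that outcome, the four minimisation factors, the listed covariates and a village random intercept. Define how each minimisation factor is coded, including the `vc_` variables.
2. Add county, or justify leaving it out.
3. For binary outcomes, name 12-month status as the dependent variable with baseline status as a covariate, and describe the result as a conditional odds ratio. It is not a difference in changes in proportion.
4. Report the SAP-text model alongside the coded one for the primary outcome and the continuous secondary outcomes.

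The cost is wording, one disclosed deviation and a few extra model runs on data already held.
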